7.7 Study Visit Management

Visit 1 (Pre-Op visit)

The patient will meet with the surgeon to discuss about their THA surgery. At this visit, the surgeon will discuss the study with the patient and will explain the advantages or disadvantages of taking

part. A copy of the Participant Informed Consent Form will be given to the patient to read and consider. The patient will be given adequate time to take the PICF home for making an informed decision about the study participation or can choose to sign the consent form during this visit. In both instances the patient will be given enough time to consider the study and request additional information from the surgeon and then provide consent. In case the patient decides to take the consent form home, the patient will return the consent form to the site after signature. One signed copy will be provided to the patient to keep. After signing the informed consent, the patient is enrolled and must be recorded on the Screening & Enrolment Log. Once the consent form is signed, the surgeon or a delegated team member will check eligibility and ensure the participant meets all criteria as per the inclusion and exclusion outlined in the study protocol. Participant demographics, primary diagnosis and relevant medical history will be recorded. All participants will then complete their pre-surgery PROMs — the Oxford Hip Score (OHS), EQ-5D-5L (EQ- VAS). Clinical assessments using standard functional parameters for physical assessment, and Harris Hip Score (including ROM) will be completed, and standard x-rays of the affected hip will be undertaken.

Visit 2 - Surgery

The dual mobility THA surgery will be performed at this visit. Intra-operative surgical details will be recorded as per standard of care including component details, and surgical approach. Deviations from the standard surgical technique will be noted. Any complications/ Adverse Events (AEs) arising from the surgery will be recorded. Any Serious Adverse Event (SAE) related to the treated hip and/or device-related incident will be recorded and reported to the Sponsor as per guidelines.

Follow Up Visit 3 (0-6 days post-surgery)

This visit will occur 0-6 days from the date of surgery while the patient is still at the hospital. Standard of care assessments will be performed which include X-rays of the treated hip. Postoperative pain management will be under the decision of the orthopaedic surgeon and support staff who will provide instructions to the patients regarding home care during the first few weeks after surgery. Medications are often prescribed for short-term pain relief after surgery. The rehabilitation program will depend on patient's goals and desired activities according to the SOC at the site. The goal of physical therapy intervention during the early post-operative phase is to decrease swelling, increase range of motion, enhance muscle control and strength in the involved lower extremity and maximize patients' mobility with a goal of functional independence.

Rehabilitation program may be individualized in function of bone quality, age, health and physical fitness of the patient. Any substantial changes to the SOC rehabilitation program will be documented. Immediate post-op complications/AEs related to the hip, or the surgery will be recorded. Any Serious Adverse Event (SAE) related to the treated hip and/or device-related incident will be recorded and reported to the Sponsor as per guidelines.

Follow Up Visits 4, 5, 6, 8, 9 and 11

The follow-up visits will be performed per the Schedule of Events table (Table 1). The study participants will be encouraged to attend site visits up to Visit 6 within the scheduled visit window to complete study assessments and questionnaires. X-rays of the treated hip will be completed as

per the schedule. When participants are unable to visit the study sites physically, participants will be encouraged to complete study questionnaires at home and provide any relevant complications/ Adverse Events information via email. When a study patient is unable to visit the study site as per the schedule of events, a protocol deviation will be reported with justification and a description of the corrective action plan to prevent a future occurrence.

Telephone Interview – Visit 7 and 10

At this contact, a designated delegated team member will telephone the participant to enquire about any complications. Any Adverse or Serious Adverse Event (SAE) or device-related incident will be recorded and reported to Corin as per guidelines. The participant will be reminded about the 10-year FU visit.

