1.0 SYNOPSIS

Study Reference	CSP2021-10				
Study Title	Clinical, radiographic and patient-reported outcomes using MobiliT cup with ECiMa insert in primary total hip arthroplasty surgery.				
Protocol Version/Date	V1.1 dated 27 September 2022				
Study Sponsor	Corin Australia Pty Ltd				
Study Purpose & Description	This Post-Market Clinical Follow (PMCF) study will evaluate clinical performance and safety outcomes of primary total hip arthroplasty surgeries using MobiliT cup with Paragon or TaperFit stem over a ten-year period. Participants will be selected for recruitment into the study from the general population of patients requiring a dual mobility total hip arthroplasty surgery and considered suitable to be implanted with MobiliT cup with Paragon or TaperFit stem (Corin Ltd). After the surgery, participants will be required to return for follow up visits and radiographic controls at specific timepoints and complete questionnaires for a period of 10 years.				
Study Objectives	 Primary Objective Evaluation of hip functional performance from baseline to 2 years after surgery. Secondary Objectives Confirmation of safety of the study devices up to 10-year follow up (FU). Evaluation of clinical outcomes and range of motion from baseline to 10-year FU. Evaluation of hip functional performance from 2 to 10 years after surgery. Assessment of health-related quality of life from baseline to 10-year FU. Evaluation of implants stability via radiographic analysis to detect evidence of migration, subsidence or loosening of the components using standard weight-bearing AP and lateral views of the treated hip from baseline to 10-year follow-up. 				
Study Endpoints	Primary Endpoint Improvement of Oxford Hip Score (OHS) from baseline (preop) to 2 years after surgery.				

	Secondary Endpoints					

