4.2 Secondary Endpoints

Secondary endpoints include:

- Revision rate of the devices under assessment after surgery to 10-year FU.
- Kaplan-Meier survival rate up after surgery to 10-year FU.
- Incidence of intraoperative and post-operative adverse events (hip, study device or surgery related) including severity and outcome up to 10-year FU.
- Change of Harris Hip Score (HHS) from preop to 10 years after surgery.
- Change of OHS from 2 to 10 years after surgery.
- Change of EQ-5-DL from preop to 10 years with previous follow-ups.
- Patient's satisfaction after surgery using the 4-point Likert-type scale at each time-point.
- Rate of continuous, progressive and symptomatic periprosthetic radiolucent lines greater than 2mm from immediate postoperative (baseline) to 2 years.

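### Section 7.7 stops encouraging site attendance at the 2-year visit and covers missed visits with volunteered email, so late adverse events and revisions may be under-ascertained

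*Protocol*

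**What the plan says.** Section 7.7 of the protocol treats Visits 4, 5, 6, 8, 9 and 11 (3 months, 1, 2, 5, 7 and 10 years) in one paragraph, and opens by placing all of them under Table 1. It then says participants will be "encouraged to attend site visits up to Visit 6 within the scheduled visit window". No matching encouragement is written for Visits 8, 9 and 11.

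For participants who cannot come, the fallback is to "complete study questionnaires at home and provide any relevant complications/ Adverse Events information via email". The paragraph ends with a rule that has no time limit: "When a study patient is unable to visit the study site as per the schedule of events, a protocol deviation will be reported".

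For the telephone contacts at 4 and 9 years (Visits 7 and 10), the same section says that "a designated delegated team member will telephone the participant to enquire about any complications".

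The synopsis states that "participants will be required to return for follow up visits and radiographic controls at specific timepoints", and puts the period at 10 years. Section 4.2 carries the safety endpoints to the same horizon: revision rate, Kaplan-Meier survival and "Incidence of intraoperative and post-operative adverse events (hip, study device or surgery related) including severity and outcome up to 10-year FU".

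Table 1 schedules complications and adverse events at every contact from surgery to 10 years. It marks HHS/ROM and X-rays as optional at 1, 5, 7 and 10 years. Section 7.3 likewise makes X-rays at those visits optional or dependent on symptoms.

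**The concern.** Two things are at issue. First, a site cannot tell from Section 7.7 whether attendance at 5, 7 and 10 years is to be pursued as actively as attendance up to 2 years. The synopsis, Table 1 and the deviation rule say that these visits are expected; the sentence on encouragement stops short of them.

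Second, the stated substitute for a missed visit relies on the participant to volunteer what seems relevant, and no staff enquiry is specified. If events are missed on that route, adverse-event incidence and revision rates are too low and device survival is too high. These are the long-term safety results that the study is meant to supply to the clinical evaluation of the devices, so an error in the favourable direction matters.

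**Working it through.** The plan states no figure for event ascertainment, so there is none to reproduce. The check is a comparison of the passages, followed by a timeline.

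**1. Is attendance expected after Visit 6?**
- Synopsis: return visits are required over the 10 years.
- Synopsis visit list and Table 1: 5, 7 and 10 years are visits; only 4 and 9 years are telephone contacts.
- Section 7.7, deviation rule: non-attendance is a deviation at any scheduled site visit, including Visits 8, 9 and 11.
- Section 7.7, encouragement: ends at Visit 6.

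The first three agree with each other. The fourth does not fit them.

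**2. What does a home-route contact ask?** Section 7.2 describes OHS as covering function and pain, EQ-5D-5L as covering five health dimensions and a health scale, and the third instrument as overall satisfaction. None, as described, asks about dislocation, revision or hip-related admission. On this route, event information therefore rests on the email. The telephone interview has staff putting the question.

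**3. Does the position change at year 2?** The email fallback itself does not; it is open at 3 months, 1 year and 2 years as well. Two other things do change after Visit 6: the encouragement stops, and HHS/ROM and X-rays, which are not optional at 2 years, become optional at 5, 7 and 10 years. The remaining outcome items in Table 1 at those visits (OHS, EQ-5D-5L, satisfaction, adverse events) can all be sent from home. More use of the home route after year 2 is a reasonable expectation, although the protocol does not state it.

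**4. Staff-led enquiry for a participant who uses the home route at every visit after Visit 6.** The remaining staff-led contacts are the calls at 4 and 9 years.
- Years 2 to 4: covered by the 4-year call, looking back 2 years.
- Years 4 to 9: covered by the 9-year call, looking back 9 − 4 = 5 years.
- Years 9 to 10: no later call. This is 1 of the 8 years after Visit 6 (12.5%).

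With the windows in Table 1 (±7 months at 9 years, ±3 months at 10 years), the last stretch runs from 12 − 7 − 3 = 2 months to 12 + 7 + 3 = 22 months.

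**5. Direction.** An event that is never reported can only lower the observed incidence or revision rate. Any shortfall therefore favours the device.

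**The case against.** The strongest reply is that the protocol keeps active follow-up in place to 10 years. Visits 8, 9 and 11 remain scheduled, and missing one is a deviation that needs a justification and a corrective action plan. Table 1 has adverse events at every contact and the scheduling of the next visit at each contact up to 9 years. The telephone calls remind the participant of the 10-year visit. Section 7.5 obliges the investigator to report all device- and hip-related events, and Section 8.4 asks for reasonable efforts to contact participants. Section 7.7 does not say that email replaces these duties.

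Much of this stands, and it rules out several stronger readings:
- A reader might infer that detection switches from staff-led to volunteered at 2 years. The text does not support this: the email route exists before year 2, and Table 1 leaves the visits between surgery and 2 years to the surgeon's standard of care.
- A reader might infer that late rates will necessarily look lower than early ones. That depends on how many participants use the home route, which the protocol does not fix.
- A reader might infer that a hip with a returned questionnaire and no email is counted as event-free. No passage says so, and censoring and time at risk belong to the SAP.
- A reader might try to size the loss. Suppose staff-led contact captures 95% of events, email captures 50–80%, and 20–60% of later contacts use the home route. If events missed by email were lost for good, capture would be 0.4 × 0.95 + 0.6 × 0.50 = 0.68 at worst and 0.8 × 0.95 + 0.2 × 0.80 = 0.92 at best. That ignores the calls. If events are spread evenly over years 2–10 and the calls recover earlier ones at 95%, capture is 7/8 × 0.95 + 1/8 × 0.68 = 0.916 to 7/8 × 0.95 + 1/8 × 0.92 = 0.946. Every input is an assumption, and the answer turns mainly on recall at the calls, so neither range is a finding.

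What the reply does not remove is the conflict of wording or the weak fallback. A deviation record documents a missed visit but does not recover event information, and an investigator can report only what reaches the site.

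**Conclusion.** The point holds as a conflict of wording with a plausible effect on late safety data. The Visit 6 limit in Section 7.7 does not agree with the synopsis, Table 1 or the deviation rule beside it. The fallback at any missed site visit is weaker than the enquiry that the study already makes at 4 and 9 years. Under-ascertainment of late adverse events and revisions is possible and would favour the device. It is most likely after the 9-year call, when a home-route participant has no further staff-led contact.

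The conclusion rests on two assumptions: that volunteered email catches fewer events than a staff member asking, and that home reporting becomes commoner once encouragement stops and examination and imaging are optional. The size cannot be determined from the protocol. This is a worthwhile, inexpensive correction, not a flaw that invalidates the 10-year endpoints.

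**What to change.** In Section 7.7:
- Reconcile the Visit 6 limit with Table 1 and the synopsis, so that attendance is encouraged for Visits 4, 5, 6, 8, 9 and 11 alike.
- Replace the email fallback. Whenever a site visit is missed, site staff run the existing Visit 7/10 telephone interview, asking about complications since the last contact, and naming dislocation, revision and hip-related admission. Home completion of the questionnaires can stay.

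The cost is a wording amendment and one short call per missed visit, using an interview that the study already runs. For the minimum of 100 hips, the ceiling over Visits 8, 9 and 11 is 3 × 100 = 300 calls, reached only if nobody attended. No visits or participants are added. A call will not reveal silent radiographic loosening, so the change improves the capture of clinical events and revisions only. How follow-up time is counted should be left to the SAP.

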8.0 PATIENT WITHDRAWAL

Patient withdrawal may occur in any study phase pre-operatively, intra-operatively, and post-operatively.

8.1 Preoperative Withdrawal

Before the surgery, the study subject may revoke consent at any time without reason or the Investigator may withdraw the subject based on preoperative test results (e.g., radiographic analysis, medical history). In this case, the subject must be excluded from the participation in the study and a study withdrawal CRF should be completed indicating the date, the reason (if available) and the last visit available. As the subject has not undergone the surgery, he/she may be substituted with the enrolment of another subject.

8.2 Intraoperative Withdrawal

If the Investigator, despite the subject selection according to criteria and the preoperative planning, notices any clinical condition or complication not compatible with the investigational devices before the first bony cut during the surgery, the subject can be withdrawn.

In this case, the subject must be excluded from the participation to the study and document the date, the reason (if available) and the last visit available on the withdrawal form. As the subject has not undergone the surgery per protocol, he/she may be substituted with the enrolment of another subject.

8.3 Postoperative Withdrawal

After the surgery, the participant may voluntarily revoke consent and withdraw from the study at any time without reason. Participants may be involuntarily exited from the study for failure to comply with the study protocol, failure to attend follow-up visits or for any clinical condition, if the Investigator deems it necessary.

In all cases, the Investigator should record the withdrawal indicating the date, the reason (if available) and the last date of follow-up available. All data obtained up to consent withdrawal will be included in the analysis.

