3.3 Design of the Study

This is a prospective, multi-centre/multi-surgeon, non-interventional, internal control, post market clinical follow up (PMCF) study. The study is post-market as all study devices are CE marked and registered in Australia. Prospective patients who are eligible for a primary hip replacement surgery with Paragon or TaperFit stem in combination with MobiliT cup, will be invited to participate in this clinical study.

This is a non-interventional clinical study as the medical devices under assessment are used in accordance with its approved labelling. The assignment of a subject to the medical devices under assessment is not decided in advance by the study protocol but falls within current clinical practice. The use of the medical devices is clearly separated from the decision to include the subject in the clinical study.

Baseline measurements (pre-operative clinical analysis and radiographic analysis at 3-month FU) will serve as internal control term during the assessment of post-surgery data.

The study will be carried out in Australia. The list of participating sites will be maintained separately from this study protocol by the Sponsor.

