8.4 Early termination due to lost to follow up or other reason

Sites should make and document reasonable efforts to contact and schedule study visits. Participants who will not or cannot return for follow-up visits as planned in the protocol will be considered as non-compliant with the study protocol. This group includes:

- Patients who are uncooperative and/or refuse to return for follow-up for three consecutive visits
- Patients who relocate without notifying the investigator and cannot be located for continued follow-up arrangements.

These patients are considered "lost to follow up".

Other reasons for early termination:

- Revision of the Study device Patients who would need a revision surgery after the primary
 dual mobility surgery will automatically be withdrawn from the study follow up as the study
 device/s will no longer be in situ. This study participant will be marked as "End of Study".
 However, any study data collected up to the revision surgery and reason for revision will be
 included in the data analysis. Data related to revisions and hip-/ procedure-/ device- related
 adverse events will be assessed as secondary objectives for this study.
- Death of a study Patient Any patient who is deceased while on the study should be marked as End of Study and thus withdrawn.

Patients who are considered "lost to follow up" or have early terminated the study must have documentation indicating the date, the reason (if available) and the last date of follow-up available.

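### Section 8.3 lets the investigator exit an operated patient for any clinical condition and makes no provision for later data, so outcome-related loss can favour the revision rate and survivorship

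*Protocol*

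**What the plan says.** Section 8.3 (Postoperative Withdrawal) covers two kinds of exit after surgery. The participant may revoke consent. Separately, the participant may be exited involuntarily for not complying with the protocol, for not attending visits, "or for any clinical condition, if the Investigator deems it necessary". The last ground has no criteria and does not exclude conditions of the study hip or the device. Because it stands apart from non-attendance, it can apply to a patient who is attending and still consents.

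On documentation, "the Investigator should record the withdrawal indicating the date, the reason (if available) and the last date of follow-up available". On analysis, "All data obtained up to consent withdrawal will be included in the analysis". No section says what is collected after an exit in which consent was not withdrawn.

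The endpoints exposed to this are long-term. Section 4.2 lists "Revision rate of the devices under assessment after surgery to 10-year FU", together with Kaplan-Meier survival and adverse events to 10 years. Section 4.1 makes the OHS improvement from before surgery to 2 years the primary endpoint. Section 3.3 describes the study as non-interventional: "The use of the medical devices is clearly separated from the decision to include the subject in the clinical study".

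**The concern.** Once the implant is in place, this study has no study-assigned treatment to stop. An investigator-initiated exit therefore acts on data collection, and after it the protocol gives no route by which a later revision or score reaches the database. Some conditions likely to prompt an exit, such as infection, recurrent dislocation or fracture, are hip events in themselves or make a later revision or a poor score more likely. Leaving follow-up can then depend on the outcome.

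Three features make this matter here:

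- There is no control arm in which similar selection might offset it.
- Kaplan-Meier estimation (section 7.4) assumes that leaving observation is unrelated to the risk of the event. The paired test in section 10.1 needs a 2-year OHS value.
- A statistical analysis plan can set a censoring rule or a missing-data method, but it cannot recover revisions and scores that were never collected. The collection rule is fixed in the protocol.

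Other withdrawal provisions are tighter. Section 8.2 limits intraoperative withdrawal to problems incompatible with the devices that are noticed before bone is cut. Section 8.4 ends follow-up at revision but preserves the event: "any study data collected up to the revision surgery and reason for revision will be" included in the analysis. A revision that follows a discretionary exit has no such protection.

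**Working it through.** **Inputs.** Section 10.2: 100 hips, OHS change 22.6, SD 9.8, two-sided alpha 0.05, power above 0.90. Section 3.1, the sponsor's series of the same cup with the standard insert: 1,100 surgeries, 62 complications, 16 revisions, 5-year Kaplan-Meier survival 95.89% (95% CI 90.08% to 98.33%). No rate of use of the clause is given, so the number of exits below is assumed.

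**Step 1: the plan's own figure.** Standardised change = 22.6/9.8 = 2.31. Exact paired t-test power (noncentral t) is above 0.999 at n = 100 and already 0.964 at n = 5. The stated power is reproduced. Losing a few hips does not threaten it, so the question is one of bias.

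**Step 2: expected events per 100 hips.**
- Complications: 62/1100 = 5.6%, so about 5 to 6 hips.
- Crude revisions: 16/1100 = 1.5%, so about 1 to 2 hips.
- At 5 years: 100 − 95.89 = 4.1, so about 4 hips. This assumes that the survival figure counts revisions; section 3.1 does not define its event.

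**Step 3: revision rate.** Let R hips be truly revised, and let h of them be exited before revision with no later capture. The crude rate is (R − h)/100 over all hips, or (R − h)/(100 − h) over those not exited.

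| R | h | over 100 | over 100 − h |
|---|---|---|---|
| 4 | 0 | 4.0% | 4.0% |
| 4 | 1 | 3.0% | 3/99 = 3.03% |
| 4 | 2 | 2.0% | 2/98 = 2.04% |
| 2 | 1 | 1.0% | 1/99 = 1.01% |

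One such exit removes a quarter of the events when R = 4 and half when R = 2. For scale, the exact 95% interval is 1.1% to 9.9% for 4/100 and 0.2% to 7.0% for 2/100. The shift lies within sampling error, but it runs in one direction and the reported interval does not reflect it.

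**Step 4: 2-year OHS.** Let the mean change over all 100 hips be 22.6, and let k exited hips have true mean change c. The mean among the rest is (100 × 22.6 − k × c)/(100 − k).

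| k | c = 10 | c = 0 |
|---|---|---|
| 2 | 2240/98 = 22.86 (+0.26) | 2260/98 = 23.06 (+0.46) |
| 5 | 2210/95 = 23.26 (+0.66) | 2260/95 = 23.79 (+1.19) |
| 10 | 2160/90 = 24.00 (+1.40) | 2260/90 = 25.11 (+2.51) |

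With five exits, roughly the number of complicated hips expected, the overstatement is about 0.7 to 1.2 points. The standard error at n = 100 is 9.8/√100 = 0.98.

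**Step 5: what is and is not lost.** Section 7.5 requires reporting of intraoperative events whatever their cause, and of postoperative events related to the device or study hip. The complication that prompts an exit is therefore recorded, as is a revision before the exit. What can be lost is what follows: later revisions, OHS, Harris Hip Score, EQ-5D-5L, satisfaction, radiographs and later adverse events.

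**The case against.** The strongest defence is that the clause has a legitimate use. Section 3.5 says that participation can involve assessments beyond usual care. Section 6.1.2 excludes people under guardianship and those whose physical or psychological state would impair participation. A patient who reaches that state after surgery, for instance through dementia, may be unable to complete the OHS, and an investigator needs some way to release that patient from assessments. This stands. It argues against simply deleting the ground, but it does not explain why revision status should also stop being collected, or why hip- and device-related conditions are not excluded.

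Second, exits are documented with date and, if available, reason, and the sponsor monitors source records (section 12.0), so clinical exits would be visible. An operated hip that leaves is not stated to be replaceable. Substitution before surgery is justified by the absence of an operation, "As the subject has not undergone the surgery, he/she may be substituted with the enrolment of another subject", and section 8.2 extends it only to patients withdrawn before bone is cut. This limits the harm, but visibility does not restore the missing outcomes.

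Third, a reader might go further and infer that the clause flatters every endpoint, that a revision after exit is never counted, or that the 10-year safety objective cannot be met. The documents do not support these readings. Intraoperative events and the triggering complication are captured. The sentence on consent withdrawal is a rule on what to include; it does not mention involuntary exit and does not bar later data, so the fault is silence and not prohibition. The protocol does not state the censoring rule. Frequency of use is unknown, and exits for conditions unrelated to the hip need not favour the device.

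**Conclusion.** The point holds as a gap in the collection rule: an open-ended investigator exit that does not exclude hip or device conditions, with nothing said about data afterwards when consent stands. It can bias the revision rate and survivorship favourably and, to a small extent, the 2-year OHS; later secondary data are exposed in the same way.

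The weight lies on revision and survivorship. With about 1 to 4 revisions expected per 100 hips, one or two exits before revision would lower the rate materially. The OHS effect is minor against 22.6 points, and the primary conclusion and its power would not change.

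These sizes assume that the sponsor's series is a fair guide, although it used the standard insert, and that its survival figure counts revisions. They also assume that exited hips go on to revision or gain only 0 to 10 OHS points. They show sensitivity to small counts and do not predict how the clause will be used. The change is worth making because it is cheap and the lost data cannot be recovered at analysis.

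**What to change.** Amend section 8.3, on data capture only:

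- A clinical condition may excuse individual assessments (a clinic visit, the Harris Hip Score, or questionnaires the patient cannot complete) but does not by itself end follow-up.
- Hip- or device-related conditions are not a ground for exit from the study.
- While consent stands, revision, adverse event and vital status continue to be collected, and OHS where the patient can complete it. The routes are the home questionnaires and email reports already allowed in section 7.7, the year 4 and year 9 telephone contacts, and site records. The telephone contacts alone would not supply the 2-year OHS.
- The sentence on data up to consent withdrawal is reconciled with exits that are not consent withdrawals.
- Investigator-initiated exits are reported with their reasons.

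The cost is a short protocol amendment and a small amount of continued site contact for a few patients, mostly through contacts that already exist.
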